4.5. Subject Replacement

Subjects who withdraw from the study post-randomisation will not be replaced.

4.6. Subject and Study Completion

A completed subject is one who has completed all phases of the study. The end of the study is defined as the date of the last subject's last visit.

Document Name	207872 Clinical Protocol.doc		
Type	Version	Document Identifier	Effective Date
elido_clinical_doc	5.0; Most-Recent; Effective; CURRENT	090032d580d488e0	30-May-2017 04:37:09
Reason For Issue	Auto Issue		

5. PRODUCT INFORMATION

5.1. Study Product

The following study products will be supplied by the Clinical Supplies Department, GSKCH:

	Test Product 1	Test Product 2	Reference Product 1	Reference Product 2
Product Name	Experimental dentifrice containing 0.454% SnF ₂ / 5% STP; 2.0% abrasive silica (RDA~58)	Experimental dentifrice containing 0.454% SnF ₂ / 5% STP; 3.5% abrasive silica (RDA~77)	Dentifrice containing 1000ppm fluoride as Sodium Monofluorophosphate (SMFP; Colgate Cavity Protection [®] , Canada Marketed dentifrice) moderate abrasivity (RDA~80)	Dentifrice containing 0.454% SnF ₂ (Sensodyne Complete Protection, Canada Marketed dentifrice) higher abrasivity (RDA~120)
Short Product Name	Test dentifrice (RDA~58)	Test dentifrice (RDA~77)	Reference dentifrice (RDA~80)	Reference dentifrice (RDA~120)
Product Formulation Code (MFC)	CCI	CCI	Commercially Available	Commercially Available
Dose	A ribbon of dentifrice, covering the length of the toothbrush head			
Route of Administration	Oral			
Dosing Instructions	Brush twice daily (morning and evening) with the allocated study dentifrice for 1 timed minute			

Other items to be supplied by the Clinical Supplies Department, GSKCH:

Name of Item	Purpose
Oral-B Sensi Soft Manual Toothbrush	Dentifrice application by tooth brushing.
Countdown timers	To ensure accurate brushing.

In addition to the test dentifrice, toothbrush and countdown timer all subjects will be supplied with a diary card/instructions. The diary card/instructions will be printed by the study site.

Document Name	207872 Clinical Protocol.doc		
Type	Version	Document Identifier	Effective Date
eido_clinical_doc	5.0; Most-Recent; Effective; CURRENT	090032d580d488e0	30-May-2017 04:37:09
Reason For Issue	Auto Issue		

5.2. Dose Schedule

During the treatment period, subjects will apply a full brush head of their allocated dentifrice, brush for one timed minute (in their usual manner) and expectorate.

The dosage regimen of twice daily treatment (morning and evening) will be applied during the treatment period. Subjects will be offered the opportunity to brush unsupervised with their allocated dentifrice at Visit 4, after completing all visit procedures.

5.3. Dose Modification

No dose modification is permitted in this study.

5.4. Product Compliance

A record of the administration of the study products will be kept using a dispensing log and the eCRF.

To ensure that subjects understand the dose of dentifrice to be used, staff will demonstrate what is meant by a 'full ribbon' (i.e. covering the length of the toothbrush head) at the baseline visit, and a supervised brushing will be carried out at Visit 3 (at the end of the visit procedures).

Subjects will receive a brushing instruction/diary sheet. This will outline the brushing instructions and will be used to record the date and time of each brushing occasion during the treatment period. Subjects will also be asked to note any missed brushings, and to use the diary to record any significant changes to diet or smoking status.

Subjects will be provided with a diary at baseline, which they will return at each visit to the study site. The number of missed or extra brushings will be recorded in the eCRF.

Subjects will also be asked to bring all tubes of study dentifrice to each study visit for a visual compliance check of each product.

5.5. Precautions

No special precautions are necessary provided the study is carried out in accordance with this protocol.

Document Name	207872 Clinical Protocol.doc		
Type	Version	Document Identifier	Effective Date
elido_clinical_doc	5.0; Most-Recent; Effective; CURRENT	090032d580d488e0	30-May-2017 04:37:09
Reason For Issue			Auto Issue

5.6. Overdose

An overdose is a deliberate or inadvertent administration of a product at a dose higher than specified in the protocol.

Overdose is not likely to occur in this study. Limited quantities of the product will be supplied, and closely monitored by the site for each subject.

Overdose per se is not an AE. However, any clinical sequelae of an overdose should be reported as an AE (and serious adverse event (SAE), if appropriate). For reporting, follow the AE and SAE reporting instructions.

5.7. Rescue Therapy

No rescue therapy is required in this study.

5.8. Product Assignment

Subjects will be assigned to study product in accordance with the randomisation schedule generated by inVentiv Health prior to the start of the study, using validated software.

5.8.1 Randomisation

A unique screening number will identify each subject screened for study participation. Screening numbers will be assigned in ascending numerical order as each subject signs their consent form. Subjects who meet all inclusion and exclusion criteria will be randomised according to the randomisation schedule. Randomisation numbers will be assigned in ascending numerical order as each subject is determined to be fully eligible.

Subjects with a sufficient level of extrinsic dental stain (in the opinion of the examiner) on the facial surfaces of the scorable anterior (maxillary and mandibular) teeth, who continue to meet all study criteria, will be stratified (based on pre-prophylaxis baseline total MLSI (A×I) score and smoking status) and randomised to treatment. The stratification factor will give rise to four strata:

- MLSI Score High, Smoker
- MLSI Score Low, Smoker
- MLSI Score High, Non Smoker

Document Name	207872 Clinical Protocol.doc		
Type	Version	Document Identifier	Effective Date
elido_clinical_doc	5.0; Most-Recent; Effective; CURRENT	090032d580d488e0	30-May-2017 04:37:09
Reason For Issue	Auto Issue		

- MLSI Score Low, Non Smoker

The randomisation list will be prepared using a randomisation block design with an equal allocation to each of the strata. The study site will receive two versions of the randomisation schedule, each in a sealed envelope and clearly marked as either “For Dispensing” or “Emergency Use Only”.

The “For Dispensing” schedule will contain the list of randomisation numbers only and will not include any coded description, just a letter A, B, C or D.

The ‘Emergency Use Only’ randomisation schedule will only be removed from the sealed envelope in an emergency situation (see Section 5.8.3). This schedule will have a randomisation number followed by the letter A, B, C or D. The schedule will have a footnote with a key for A, B, C and D identifying the three treatments.

However, to maintain the blinding of the study as far as possible, all treatment allocations for all randomisation numbers on this randomisation schedule will be masked with scratch-off panels. Only the panels required for the unblinding the particular subject should be removed.

5.8.2. Blinding

The study statistician, other employees of the sponsor, and vendors acting on behalf of the sponsor, who may influence study outcomes are blinded to the product allocation of subjects. The examiner will be blinded to the treatment received. To ensure the examiner remains blinded throughout the study, the examiner is not permitted in the room whilst product is dispensed, and subjects will be asked not to remove study products from their bags outside of the dispensing room and until they are home. In addition, subjects should be treated in a separate area. The dispensing staff will not be involved in any efficacy assessments during the study.

5.8.3. Code Breaks

The blind must only be broken in an emergency where it is essential to know which product a subject received in order to give the appropriate medical care. Wherever possible the Investigator (or designee) must contact the Sponsor prior to breaking the blind. The investigator must document the reason for breaking the code and sign and date the appropriate document.

The randomisation schedules must be returned to GSKCH at the end of the study.

Document Name	207872 Clinical Protocol.doc		
Type	Version	Document Identifier	Effective Date
elido_clinical_doc	5.0; Most-Recent; Effective; CURRENT	090032d580d488e0	30-May-2017 04:37:09
Reason For Issue	Auto Issue		

5.9. Packaging and Labelling

The reference dentifrices (Colgate Cavity Protection® and Sensodyne Complete Protection) will be sourced from the Canadian market. The test dentifrices will be manufactured, filled and supplied by GSKCH.

All dentifrices, will be overwrapped in white vinyl to obscure any branding on the commercial packs. Each tube will have one English label and one French label affixed. Each subject will receive a sufficient number of tubes to cover usage during the treatment phase.

The contents of the label will be in accordance with all applicable regulatory requirements and will be the responsibility of the Clinical Supplies Department, GSKCH.

All sundry items will be supplied in their commercial packaging for dispensing by study staff as required.

Care should be taken with the supplied products and their labels so that they are maintained in good condition. It is important that all labels remain intact and legible for the duration of the study. Subjects should be instructed to not remove or deface any part of the study label.

5.9.1. Accountability of Product

All products supplied are for use only in this clinical study and should not be used for any other purpose.

Completion of diaries will be the responsibility of subjects, after they have been dispensed subjects will be asked to take them home and bring them back to the clinical site for each study visit.

The investigator or designee will maintain a full record of study product accountability. A Product Dispensing Log must be kept current and will contain the following information:

- The identification of the subject to whom the study product was dispensed.
- The dates and quantity of the study product dispensed to the subject.
- The dates and quantity of the study product returned by the subject (if applicable).

Document Name	207872 Clinical Protocol.doc		
Type	Version	Document Identifier	Effective Date
elido_clinical_doc	5.0; Most-Recent; Effective; CURRENT	090032d580d488e0	30-May-2017 04:37:09
Reason For Issue	Auto Issue		

The inventory must be available for inspection by the study monitor during the study. At the end of the study, study product supplies will be verified by the monitor. Study product supplies will then be either collected by the study monitor or returned by the investigator or designee to the GSKCH Clinical Supplies Department or designated vendor.

5.9.2. Storage of Product

Study product supplies must be stored in compliance with the label requirements in a secure place with limited or controlled access.

6. STUDY ASSESSMENTS AND PROCEDURES

This section lists the procedures and parameters of each planned study assessment. The exact timing of each assessment is listed in the Schedule of Events section.

Adherence to the study design requirements, including all assessments and procedures are essential and required for study conduct.

6.1. Visit 1 - Screening Visit

6.1.1. Telephone Screening

Prior to the screening visit, telephone screening of interested subjects will be conducted using a telephone script. This will be conducted by the site recruitment staff or designee.

6.1.2. Informed Consent

The investigator, or designee, must obtain written (signed and dated by the subject) informed consent from each subject participating in this study after adequate explanation of the aims, methods, objectives, and potential hazards of the study.

The investigator, or designee, must also explain to the subjects that they are completely free to refuse to enter the study or to withdraw from it at any time. Appropriate forms for documenting a written consent will be provided by the investigator or by GSKCH. The investigator, or designee, should sign and date the consent form to confirm that the consent process was completed correctly. The subject will be provided with a copy of their signed and dated consent form and any other written information which they should be instructed to retain.

Document Name	207872 Clinical Protocol.doc		
Type	Version	Document Identifier	Effective Date
elido_clinical_doc	5.0; Most-Recent; Effective; CURRENT	090032d580d488e0	30-May-2017 04:37:09
Reason For Issue			Auto Issue

If, during a subject's participation in the study, any new information becomes available that may affect the subject's willingness to participate in the study, each ongoing subject should receive a copy of this new information and be re-consented into the study. Subjects should be provided with a copy of the signed and dated amended consent form. The date of consent will be recorded on the eCRF.

6.1.3. Demographics

The following demographic detail will be captured by the Investigator or designee and recorded on the eCRF: year of birth, gender and race.

6.1.4. Medical History and Concomitant Medication

Medical history will be assessed as related to the inclusion/exclusion criteria by the Investigator or medically qualified designee. Details of any relevant dental, medical or surgical history (within the last year), including allergies or drug sensitivity, will be recorded on the eCRF. Any concomitant therapy taken in the 30 days prior to the Screening Visit and throughout the study will also be recorded.

6.1.5. Oral Soft Tissue (OST) Examination

Where possible, this procedure should be conducted by a single trained dental examiner. The examination will be accomplished by direct observation and palpation with retraction aids as appropriate. The examiner will include examination of the Labial Mucosa (including lips), Buccal Mucosa, and Mucogingival folds, Gingival Mucosa, Hard Palate, Soft Palate, Tonsilar Area, Pharyngeal Area, Tongue, Sublingual Area, Submandibular Area and Salivary Glands. The results of the examination will be recorded in the eCRF as either normal or abnormal with details of any abnormalities. A brief description of any abnormality observed by the examiner or reported by the subject at the application site following dental prophylaxis or administration of the treatment dentifrices will be recorded as an AE.

An OST examination will be conducted at Visits 1 and 2, prior to any clinical assessments. While it is preferable to use the same OST examiner throughout the study, to facilitate subject flow, OST examinations may be carried out by different examiners.

Document Name	207872 Clinical Protocol.doc		
Type	Version	Document Identifier	Effective Date
elido_clinical_doc	5.0; Most-Recent; Effective; CURRENT	090032d580d488e0	30-May-2017 04:37:09
Reason For Issue	Auto Issue		

6.1.6. Full Oral Hard Tissue (OHT) Visual Examination

A suitable qualified individual will perform an examination of the oral hard tissue to confirm that the subject has a minimum of 16 natural teeth and to evaluate dentition exclusions. The examination will be performed by direct observation.

6.1.7. Visual MLSI Stain Assessment

A visual assessment of the 12 anterior teeth for stain will be performed (individual tooth scores will not be recorded) to determine eligibility. Eligible subjects will be deemed to have a sufficient level of extrinsic dental stain (in the opinion of the examiner) on the scorable surfaces of the anterior (maxillary and mandibular) teeth.

6.2. Visit 2 - Baseline Visit

6.2.1. Oral Soft Tissue (OST) Examination

Complete as described in Section 6.1.5.

6.2.2. Full Oral Hard Tissue (OHT) Examination

Complete as described in Section 6.1.6.

6.2.3. Full MLSI Stain Assessment

Stain assessments will be performed by a single clinical examiner, in the same room with consistent light levels, throughout the study to facilitate standardisation of the assessments. Subjects will brush their anterior teeth with a wetted toothbrush for 30 seconds prior to each stain assessment. Teeth will be air dried prior to the assessment, and during the assessment as needed.

The facial and lingual surfaces of each assessable tooth is divided into four regions. The 'gingival' region is defined as a crescent-shaped band, approximately 2 mm wide, adjacent to the free margin of the gingiva and extending to the crest of the interdental papillae of the adjacent teeth. The 'body' of the tooth is then sub-divided into three regions on the facial surfaces.

- **Maxillary and mandibular facial surfaces:** distal facial area; body facial area; mesial facial area
- **Mandibular lingual surfaces:** distal lingual area; body lingual area; mesial lingual area

Document Name	207872 Clinical Protocol.doc		
Type	Version	Document Identifier	Effective Date
elido_clinical_doc	5.0; Most-Recent; Effective; CURRENT	090032d580d488e0	30-May-2017 04:37:09
Reason For Issue	Auto Issue		

Extrinsic dental stain will be scored in each area using the MLSI [MacPherson, 2000], with grades of 0-3 assigned for each category of intensity and area.

Stain Intensity: intensity will be scored separately for the 'gingival' and 'body' areas of each assessable tooth as follows.

- Score 0 = No stain
- Score 1 = Light stain
- Score 2 = Moderate stain
- Score 3 = Heavy stain

Stain Area: area will be scored separately for the 'gingival' and 'body' areas of each assessable tooth as follows.

- Score 0 = No stain
- Score 1 = Stain covering up to 1/3 of region
- Score 2 = Stain covering up to 1/3 of region, and no more than 2/3 of region
- Score 3 = Stain covering more than 2/3 of region

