This is a single-centre, examiner-blind, randomised, four treatment, parallel group study, stratified by baseline total MLSI (A×I) score for the facial surfaces of at least 11 of the 12 anterior teeth (<45 (low); ≥45 (high)) and smoking status (smoker; non smoker). A single dental examiner will perform a full MLSI assessment of the area and intensity of extrinsic dental stain on the facial surfaces of the 6 maxillary and 6 mandibular anterior teeth (universal numbering: 6-11 and 22-27), and the lingual surfaces of the 6 mandibular anterior teeth (universal numbering: 22-27), at baseline (Visit 2), and following 2 and 4 weeks twice daily brushing (Visits 3 and 4).

Potential subjects will be pre-screened via telephone and later attend a screening visit during which they will give their written informed consent to participate in the study. Demography, medical history and concomitant medications will be recorded, followed by an oral examination. This will include an oral soft tissue (OST) examination, a full oral hard tissue (OHT) examination and a visual MLSI stain assessment. Subjects deemed (in the opinion of the examiner) to have a sufficient level of extrinsic dental staining (assessed to be formed due to ingestion of food or drinks, or use of tobacco products) on the facial surfaces of the scorable anterior (maxillary and mandibular) teeth, as well as meeting all other study criteria, will be considered as eligible to proceed with the study. Eligible subjects will continue to use their own dentifrice at home until their baseline visit. Prior to the baseline visit, subjects will be asked to abstain from oral hygiene for at least 6 hours.

At baseline, each subject will undergo an OST and a full OHT, and then brush their anterior teeth for 30 seconds using a wetted toothbrush (with tap water), prior to undergoing a full MLSI stain assessment. Subjects deemed (in the opinion of the examiner) to have a sufficient level of extrinsic dental stain on the facial surfaces of the scorable anterior (maxillary and mandibular) teeth, who continue to meet all study criteria, will be stratified (based on pre-prophylaxis baseline total MLSI (A×I) score and smoking status) and randomised to treatment. The stratification factor will give rise to four strata:

- MLSI Score High (≥45), Smoker
- MLSI Score Low (<45), Smoker
- MLSI Score High (≥45), Non Smoker
- MLSI Score Low (<45), Non Smoker

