4.4 Analysis of Efficacy

4.4.1 Primary Efficacy Endpoint

4.4.1.1 Primary Efficacy Endpoint Definition

The primary endpoint is the Week 4 overall MLSI (A×I).

Each tooth site will be evaluated for stain level and will be assigned an intensity score (I) and an area score (A) by the examiner. Overall MLSI (A×I) score for each subject at each visit (Baseline, Week 2 and Week 4) is calculated as the mean MLSI (A×I) score over all gingival, body, mesial and distal sites on the facial surfaces of the six maxillary anterior teeth and six mandibular anterior teeth, and the lingual surfaces of the six mandibular anterior teeth. It is

possible that some sites could have missing values, in that case the mean is calculated over all non-missing sites

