4.8 Analysis of Other Variables

There will be ten subjects selected for repeated MLSI assessments to test the consistency of the examiner. .

The repeat MLSI area and intensity assessments will be cross tabulated ([Table 14.2.5.1](#) and [Table 14.2.5.2](#)) and compared to the original assessments and will not be used in any efficacy analysis. A weighted Kappa coefficient (κ), along with the 95% CI will be calculated to assess the intra-examiner reliability. Fleiss-Cohen weighted kappa will be calculated for the repeatability analysis. Reliability will be deemed

- Excellent if $\kappa > 0.75$
- Fair to good if $0.4 \leq \kappa \leq 0.75$
- Poor if $\kappa < 0.4$

All subjects who have repeatability data will be included in this analysis.

5 Changes to the Protocol Defined Statistical Analysis Plan

There is an additional analysis to the originally planned statistical analysis specified in the [protocol version 5.0 \[\(Dated: 30/May/2017\)\]](#). This additional analysis is the repeatability analysis described in Section 4.7.

6 References

Lobene RR. Effect of Dentifrices on Tooth Stains with Controlled Brushing. *Journal of American Dentistry* 1968: 77; 849-855.

[figure not shown]
CCI

207872

Statistical Reporting and Analysis plan, 24 Aug 2017

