[1] From ANCOVA with treatment and smoking status as factors and baseline [variable] score as covariate

CCI

207782

Statistical Reporting and Analysis plan, 24 Aug 2017

[2] Difference is first named treatment minus second named treatment such that a negative difference favours the first named treatment

Page x of y

PPD

CCI

207782

Statistical Reporting and Analysis plan, 24 Aug 2017

Protocol 207872

Program Run Date:xxxx

Table 14.2.5.1
Repeatability for MLSI Intensity Score
Repeatability Population

Repeatability Population (N=XX)

Initial \ Repeated	Missing	0	1	2	3
Missing	xx	xx	xx	xx	xx
0	xx	xx	xx	xx	xx
1	xx	xx	xx	xx	xx
2	xx	xx	xx	xx	xx
3	xx	xx	xx	xx	xx
Kappa	0.xx				
95% CI	(0.xx, 0.xx)				

Intensity Score: 0=No Stain; 1=light Stain; 2=Moderate Stain; 3=Heavy Stain. Missing means non-scorable.

Page x of y

PPD

Note to Programmer: For Table 14.2.5.2, use area scoring descriptions in footnote.

CCI

207782

Statistical Reporting and Analysis plan, 24 Aug 2017

Protocol 207872

Program Run Date:xxxx

Table 14.3.1.1
Treatment Emergent Adverse Event by System Organ Class and Preferred Term
Safety Population

Safety Population (N=xx)										
System Organ Class	Test Dentifrice (RDA-58)		Test Dentifrice (RDA-77)		Reference Dentifrice (RDA-80)		Reference Dentifrice (RDA-120)		Overall (N=XX)	
Preferred Term	(N=XX)		(N=XX)		(N=xx)		(N=xx)			
	n (%)	nAE	n (%)	nAE	n (%)	nAE	n (%)	nAE	n (%)	nAE
NUMBER OF SUBJECTS WITH AT LEAST ONE AE	xx (xx.x)	xx	xx (xx.x)	xx	xx (xx.x)	xx	xx (xx.x)	xx	xx (xx.x)	xx
NUMBER OF SUBJECTS WITH NO AE	xx (xx.x)	xx	xx (xx.x)	xx	xx (xx.x)	xx	xx (xx.x)	xx	xx (xx.x)	xx
SKIN AND SUBCUTANEOUS TISSUE DISORDERS	xx (xx.x)	xx	xx (xx.x)	xx	xx (xx.x)	xx	xx (xx.x)	xx	xx (xx.x)	xx
ERYTHEMA	xx (xx.x)	xx	xx (xx.x)	xx	xx (xx.x)	xx	xx (xx.x)	xx	xx (xx.x)	xx
DERMATITIS	xx (xx.x)	xx	xx (xx.x)	xx	xx (xx.x)	xx	xx (xx.x)	xx	xx (xx.x)	xx
GASTROINTESTINAL SYSTEM	xx (xx.x)	xx	xx (xx.x)	xx	xx (xx.x)	xx	xx (xx.x)	xx	xx (xx.x)	xx
ABDOMINAL PAIN	xx (xx.x)	xx	xx (xx.x)	xx	xx (xx.x)	xx	xx (xx.x)	xx	xx (xx.x)	xx
DRY MOUTH	xx (xx.x)	xx	xx (xx.x)	xx	xx (xx.x)	xx	xx (xx.x)	xx	xx (xx.x)	xx
VOMITTING	xx (xx.x)	xx	xx (xx.x)	xx	xx (xx.x)	xx	xx (xx.x)	xx	xx (xx.x)	xx
Etc.										

n (%) = Number (percent) of subjects nAE = Number of adverse events.

Page x of y

PPD

Note to Programmer: For Table 14.3.1.2, change 'System Organ Class' to 'Oral/Non-Oral'

CCI

207782

Statistical Reporting and Analysis plan, 24 Aug 2017

Protocol 207782

Program Run Date:xxxx

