Statistical Reporting and Analysis plan, 24 Aug 2017

Protocol 207872

Program Run Date:xxxx

Listing 16.2.5.2
Concomitant Medications and Significant Non-drug Therapies Taken During Treatment
Randomised Population

Treatment Group: Test Dentifrice (RDA-58)

Subject Number	Age/Sex/Race[1]	Sequence Number	Treatment	Reason for Treatment	Frequency	Start Date	Ongoing? (Yes/No)
PPD			xxxxx	xxxxxx	xx	PPD	

[1] Age in years; Sex: F = Female, M = Male; Race: A = Asian, B = Black or African American, I = American Indian or Alaska Native, H = Native Hawaiian or Other Pacific Islander, W = White, M = Multiple.

PPD

CCI

207782

Statistical Reporting and Analysis plan, 24 Aug 2017

Protocol 207872

Program Run Date:xxxx

Listing 16.2.6.1
MLSI Stain Index
Randomised Population

Treatment Group: Test Dentifrice (RDA-58)

Subject Number	Age/Sex/Race[1]	Visit	Tooth Number (universal/FDI)	Surface	Site	Intensity (I) Score[2]	Area (A) Score[3]	AXI Score
PPD						x	x	x

[1] Age in years; Sex: F = Female, M = Male; Race: A = Asian, B = Black or African American, I = American Indian or Alaska Native, H = Native Hawaiian or Other Pacific Islander, W = White, M = Multiple.

[2] Intensity Index: 0=No Stain; 1=light Stain;2=Moderate Stain; 3=Heavy Stain. Missing means non-scorable; X=Missing.

[3] Area Index: 0=No Stain; 1=Stain covering upto 1/3 of region; 2=Stain covering upto 1/3 of region, and no more than 2/3 of region ; 3=Stain covering more than 2/3 of region; X=Missing

PPD

CCI

207782

Statistical Reporting and Analysis plan, 24 Aug 2017

Protocol 207872

Program Run Date:xxxx

Listing 16.2.6.2
Overall MLSI Stain Score
Randomised Population

Treatment Group: Test Dentifrice (RDA-58)

Subject Number	Age/Sex/Race[1]	Visit	Overall MLSI (AXI) Score [2]	Overall Interproximal MLSI (AXI) Score [3]	Overall MLSI Area (A) Score [2]	Overall MLSI Intensity (I) Score [2]
PPD			x.xx	x.xx	x.xx	x.xx

[1] Age in years; Sex: F = Female, M = Male; Race: A = Asian, B = Black or African American, I = American Indian or Alaska Native, H = Native Hawaiian or Other Pacific Islander, W = White, M = Multiple.

[2] Overall score is the mean over all assessed tooth sites.

[3] Overall interproximal score is the mean over all interproximal tooth sites.

PPD

CCI

207782

Statistical Reporting and Analysis plan, 24 Aug 2017

Protocol 207872

Program Run Date:xxxx

Listing 16.2.7.1
All Adverse Events
Randomised Population

Treatment Group: Test Dentifrice (RDA-58)

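### MLSI area score 2 is worded so that it overlaps score 1 and leaves coverage above 1/3 and up to 2/3 without a score

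*Protocol*

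**What the plan says.** Protocol 6.2.3 grades stain area from 0 to 3 in each region of each assessable surface, with 0 for no stain. The middle grade is given as "Score 2 = Stain covering up to 1/3 of region, and no more than 2/3 of region". The grade below it, the lowest for a stained region, is worded "Score 1 = Stain covering up to 1/3 of region". At the top of the scale the protocol has "Score 3 = Stain covering more than 2/3 of region".

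The section cites the published index but gives no other description of the grades. In the SAP, footnote 3 of Listing 16.2.6.1 carries the same definition of the middle grade: "2=Stain covering upto 1/3 of region, and no more than 2/3 of region". A programmer note under the Table 14.2.5.1 shell adds "For Table 14.2.5.2, use area scoring descriptions in footnote". No section of either document defines score 2 differently.

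The area grade is used in several places. SAP 4.4.1.1 has the primary score "calculated as the mean MLSI (A×I) score over all gingival, body, mesial and distal sites". SAP 4.4.3 lists the interproximal A×I score and the mean area score at Weeks 2 and 4 as exploratory variables. Protocol 3.1 stratifies randomisation on the total facial A×I score, low below 45 and high from 45 upwards. SAP 4.8 states "The repeat MLSI area and intensity assessments will be cross tabulated", with a weighted kappa.

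**The concern.** An ordinal scale should give every possible observation exactly one grade. This one does not. The lower limit of score 2 has been written as an upper limit, so the two conditions in score 2 reduce to coverage of one third or less, which is score 1 again. Nothing then covers the middle third.

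The defect sits in an operative definition. Area is one of the two factors in the primary endpoint and in the stratification total, and it stands alone in the area endpoint and the area kappa. An examiner following the text literally would have a choice of grades for lightly covered regions and no grade for moderately covered ones. A middle-third region left blank would also drop out of the subject's mean, because SAP 4.4.1.1 averages over non-missing sites.

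The risks are added noise if the reading changes during the study, a shifted scale if one wrong reading is held throughout, and some subjects placed in the wrong stratum.

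**Working it through.** **Coverage of the scale.** Let c be the fraction of a region that is stained. The definitions in Protocol 6.2.3, taken as written, are compared below with score 2 read as more than 1/3 and no more than 2/3.

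| Coverage | Grades met as written | Grades met with score 2 corrected |
|---|---|---|
| c = 0 | 0 | 0 |
| 0 < c ≤ 1/3 | 1 and 2 | 1 |
| 1/3 < c ≤ 2/3 | none | 2 |
| c > 2/3 | 3 | 3 |

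Applying the written definitions to c in steps of 1/300 gives, for the 300 non-zero values:

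- 100 meet two grades (1/300 to 1/3)
- 100 meet none (101/300 to 2/3)
- 100 meet score 3 only

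With the corrected score 2, each of the 300 values meets exactly one grade, 100 per grade.

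**Number of sites.** There are 12 facial and 6 mandibular lingual surfaces with four sites each (Protocol 3.1 and 6.2.3).

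- Overall score: (12 + 6) × 4 = 72 sites
- Facial total: 12 × 4 = 48 sites

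**Effect of one region in the overlap.** Reading area as 2 instead of 1 changes A×I from 1 × I to 2 × I, a difference of I, where I is 1, 2 or 3.

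| Intensity I | Change in A×I and in facial total | Change in overall mean (72 sites) |
|---|---|---|
| 1 | 1 | 1/72 = 0.014 |
| 2 | 2 | 2/72 = 0.028 |
| 3 | 3 | 3/72 = 0.042 |

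**Stratum boundary.** A constructed example: a subject with a facial total of 40 has five lightly stained regions (I = 1) read as area 2 instead of 1. The total becomes 40 + 5 × 1 = 45, which moves the subject from the low to the high stratum.

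These figures follow from the wording. They do not estimate how often a region would be misread.

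**The case against.** The strongest reply is that the slip corrects itself. The scale is ordered, score 1 ends at one third, score 3 starts above two thirds, and score 2 itself names two thirds as its limit. Only the middle third is left. The section also directs the examiner to a published index that the protocol treats as established, so an experienced examiner is unlikely to grade a region with one third coverage or less as 2. This stands, and it is the main reason to expect little or no practical effect.

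The design limits the damage further. One examiner, blinded to treatment, scores every subject at every visit, so a misreading should fall on all arms alike. The pre-prophylaxis score is taken before randomisation, so a misreading held consistently would only move the effective cut, and randomisation within strata would remain valid. The ANCOVA adjusts for smoking status and the continuous baseline score, and the low/high stratum is not a model term. The study is an exploratory proof of principle without formal power. All of this stands.

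The repeat examinations protect less. There are 30 in all, with 10 to 30 minutes between the paired scorings. They can expose inconsistent grading within a session, but not a wrong reading that is held consistently.

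It is also fair to say that no shell for Table 14.2.5.2 is shown. That the wording would reach that table is inferred from the programmer note. None of these points makes the written definition usable as it stands.

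**Conclusion.** The definition of area score 2 is wrong as written, in the protocol and in the SAP. It duplicates score 1 and leaves a third of the coverage range without a grade. This is a drafting error in an operative definition and should be fixed. It does not put the design or the analysis in doubt.

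The effect on the results cannot be quantified from the documents. The per-region sizes above assume that all 72 sites are scored and that the region is read as 2 where 1 was meant. With fewer scored sites the shift in the mean per region is slightly larger. Bias between arms is unlikely as long as the one examiner remains blinded. That the error is a slip for more than 1/3 is an inference from scores 1 and 3, and it needs no outside source.

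**What to change.** State area score 2 as stain covering more than 1/3 and no more than 2/3 of the region in Protocol 6.2.3 and in footnote 3 of SAP Listing 16.2.6.1. Use the same text when the footnote of Table 14.2.5.2 is built. Check that the eCRF and any scoring material given to the examiner carry the same definition.

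The cost is one line in the protocol, the one or two SAP footnotes, and a short check of the data collection material. Design, sample size and analysis do not change.
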